## 8.2. The Number of Participants

40 participants will be recruited (20 in the intervention group, 20 in the control group).

According to Connelly (2008), extant literature suggests that a pilot study sample should be 10% of the sample projected for the larger parent study. [26] Isaac and Michael (1995) suggested 10 - 30 participants [27]; Hill (1998) suggested 10 to 30 participants for pilots in survey research [28]; Julious (2005) in the medical field [29] and van Belle (2002) suggested 12 [30]; Treece and Treece (1982) suggested 10% of the project sample size. [31]

Existing studies of reference used the following sample sizes:

Welschen et al (2012) [17]: 261

Asimakopoulou et al (2008) [24]: 95

Tawfik & Mohamed (2016) [25]: 180

Based on these observations, we decided to take the size of the bigger sample as reference (n=261) and to apply the 10% rule. However, in order to allow for drop-outs and facilitate comparison between the two arms, we decided to add a margin and target 40 participants in total.

## 8.3. Analysis of Outcome Measures

We will analyse the following outcome variables:

- Feasibility of a larger study: in order to inform the design of a larger study, we will assess the following criteria: integrity of study protocol, consent rate, acceptability of intervention, expected impact of intervention.
- Appropriateness of risk perceptions: we will compare participants' perceived risks to their personalised risk estimates computed via a validated simulation model (UKPDS-OM [32]).
- Self-management scores: we will assess participants' adherence to self-care activities using two validated questionnaires: 1) The Summary of Diabetes Self-Care Activities Measure (SDSCA) [23]; 2) The 8-Item Morisky Medication Adherence Scale (MMAS-8) [33]

## 9. DATA MANAGEMENT

### 9.1. Access to Data

Direct access will be granted to authorised representatives from the Sponsor and host institution for monitoring and/or audit of the study to ensure compliance with regulations.

### 9.2. Data Recording and Record Keeping

Data will be anonymised and no participant will be identifiable from the data in the possession of the researchers, outside of the CI and the direct care team. Participants will be linked to an ID number that will be used by the CI to give feedback to the GP after study.

Anonymised research data will be recorded and stored numerically (University password-protected computers), managed by [name], for the duration of the project. Only the researchers involved in the project will have access to the data. Data may be kept up to 5 years following the publication of research findings in University locked up cupboards. Data may also be used to inform the design of a larger trial before publication of research findings and be included in the analysis of this larger trial.

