Recent studies have shown that people with T2DM largely underestimate their risks of developing complications. [15] Existing risk communication interventions have shown mixed results, with many participants barely understanding the explanations of health professionals about risks and having poor recall of risk information [16-18]. In this context, there is a need for better risk communication interventions. [15] Rather than increasing the quantity of information to be communicated ('less is often more' [19]), it is necessary to improve its quality. New interventions that make use of patients' decision-making biases are considered to be very promising in the risk communication field [20-22]. We believe that such interventions, through which personalised risks are communicated, will help to correct erroneous risk perceptions, and, in turn, have a greater impact on self-care behaviours.

Based on the results of recent studies investigating the risk perceptions and risk attitudes of people with T2DM, we have developed a new, tailored risk communication intervention. This intervention aims to increase patients' awareness of their risks for complications associated with T2DM and, in turn, to encourage the adoption of recommended self-care behaviours. The objectives of the full trial are to assess the feasibility and measure the expected impact of such an intervention, in order to inform the design of a larger study (RCT to be conducted in the future).

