### **7.3. Procedure**

- Visit 1

For participants who gave their informed consent, the CI will administer the study questionnaires that measures risk perceptions and assesses self-management behaviour (~10 minutes). [23, 33]

After the first set of questionnaires are completed, all participants will attend their routine clinical consultation with their GP. During the consultation, half of the participants will receive the risk communication intervention from the GP (intervention group, ~5 minutes) and half of the participants will not (control group). Participants will be randomised into the intervention or the control group by means of a list drawn up by a computerised randomisation program. They will be attributed with an order number and this number will be randomly allocated into one of the two groups. The participant will be blind to their allocation but the CI will not be.

Right after the consultation, risk perceptions of all participants (i.e. in both groups) will be measured by the CI once again (~5 minutes), to account for potential effect of the consultation on the control group.

- Visit 2

At participants' next consultation visit, which will be approximately 12 weeks after the intervention, the same questions about risk perceptions and self-management behaviour will be asked by the CI right before the consultation (~10 minutes).

The interest of face-to-face appointments is that it ensures reliability in participants' answers, as compared to email or telephone interviews.

This methodology has been used in most recent studies that aimed at measuring the impact of risk communication interventions. [17, 24, 25]

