### **8. STATISTICS AND ANALYSIS**

#### **8.1. Description of Statistical Methods**

Frequencies and percentages will be used to describe categorical variables, and means  $\pm$  SD to describe continuous variables.

Pre-post intervention differences between groups in terms of study outcome variables will be tested using Chi-square and Student t-tests, whereas pre-post intervention differences within groups will be tested using McNemar and paired t-tests.

The Kappa test will be used for detecting the degree of agreement between pre- and post-perceived risk with baseline objective risk.

In the intervention group, correlation between appropriateness of risk perceptions and self-management scores (post-intervention) will be tested by means of point biserial correlation. Finally, Pearson and Spearman correlations will be used to test for correlations between observable characteristics and outcome variables.

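### Does section 9.2 need a rule for when pilot data may be pooled into the larger trial's analysis?

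*Combined protocol and SAP*

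**What the plan says.** Section 9.2 (Data Recording and Record Keeping) covers anonymisation, storage and retention. It ends with a permission: "Data may also be used to inform the design of a larger trial before publication of research findings and be included in the analysis" of the larger trial. The verb is permissive. No method of inclusion is named and no condition is attached.

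The larger trial is a separate, future study. Section 3 says the present work is done "in order to inform the design of a larger study (RCT to be conducted in the future"). The documents give no endpoint, size or significance level for it.

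The pilot effect is meant to feed that design. Section 3 says the aim is to "assess the feasibility and measure the expected impact of such an intervention, in order to inform the design of a larger study". Section 8.3 lists the feasibility criteria as "integrity of study protocol, consent rate, acceptability of intervention, expected impact of intervention". Section 8.1 tests the outcomes by arm: "Pre-post intervention differences between groups in terms of study outcome variables will be tested using Chi-square and Student t-tests". Section 8.3 offers more than one candidate endpoint: appropriateness of risk perceptions, and "adherence to self-care activities using two validated questionnaires". On blinding, section 7.3 says "The participant will be blind to their allocation but the CI will not be"; the CI also administers the questionnaires.

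**The concern.** The same 40 patients may be used twice: once to shape the larger trial, and once as evidence in its analysis. If the shaping is independent of the observed effect, double use is harmless. If the later trial's endpoint, its size, or the decision to pool follows the pilot result, the pilot contribution to the pooled statistic is selected, and an ordinary test does not allow for that.

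The protocol itself opens this route. Expected impact is a design input, comparisons by arm will be run, several scores are available, and the person collecting the data knows the allocation. No section says when pooling is decided or what may be known at that time. The larger trial's protocol will probably be completed after results by arm exist. A sentence added now, while nothing has been seen, looks like a cheap safeguard. At stake is the type I error of the later trial; no figure in the pilot is affected.

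**Working it through.** **Inputs.** Pilot size 40, 20 per arm (section 8.2). The documents state no size for the larger trial. I assume a total of 261 including the pilot; this is the size of the reference study in section 8.2, used there only for the 10% rule (0.10 × 261 = 26.1, raised to 40 by an unquantified margin). Also assumed: two-sided 5%, the same endpoint and variance in both parts, all 40 evaluable, and each selection rule below. The plan gives no pooling figure to reproduce.

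**Model.** With Z1 the pilot statistic and Z2 that of the new patients, independent under the null, the naive pooled statistic is

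Z = √t·Z1 + √(1−t)·Z2, with t = 40/261 = 0.153, √t = 0.391, √(1−t) = 0.920,

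and the null is rejected if |Z| > 1.96. Results are from 4 million draws under the null. Ranges cover correlations between scores from 0.6 to 0.

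| Rule in the later trial | Two-sided error | Favourable direction (nominal 2.5%) |
|---|---|---|
| Nothing depends on the pilot effect | 5.0% | 2.5% |
| Pool only if pilot favourable, else new data only | 5.0% | 3.3% |
| Endpoint = more favourable of two | 5.0% | 3.3–3.7% |
| Endpoint = larger absolute effect of two | 5.9–6.1% | 2.9–3.0% |
| Endpoint = most favourable of three | 5.2–5.5% | 3.8–4.6% |
| Endpoint = largest absolute effect of three | 6.5–6.9% | 3.2–3.5% |
| Re-size on pilot effect, total limited to 200–400 | 5.3% | 2.8% |
| Same, limited to 100–400 | 5.7% | 3.3% |
| Same, limited to 60–400 | 6.1% | 3.7% |

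Re-sizing takes d = 2·Z1/√40 and N = 4 × 2.8016²/d² (80% power), held within the limits, with the upper limit used if d ≤ 0.

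**Reading the table.** The highest two-sided figures need an endpoint chosen on the absolute effect, so that a harmful-looking score could be picked. That is unlikely here, since the intervention aims at improvement and section 7.5 calls a negative effect unlikely. The 6.1% for re-sizing needs a total as low as 60, only 60 − 40 = 20 new patients. The total matters: for the largest absolute effect of three uncorrelated scores, error is 9.0% at 120, 7.5% at 200 and 6.2% at 400.

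**Cost of a rule written now.** A strict rule would admit pilot outcomes only if the endpoint and the commitment to pool were fixed before any comparison by arm, and would otherwise exclude them. At the effect that gives 80% power with all N, power without the 40 is Φ(2.8016·√(1 − 40/N) − 1.96):

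- N = 200: 71%
- N = 261: Φ(2.8016 × 0.920 − 1.96) = Φ(0.618) = 73%
- N = 400: 76%

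The standard error at 261 widens by 1/0.920 = 1.087, about 9%.

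**Would such a rule be complete?** Fixing the endpoint, the size and the commitment to pool does not cover the decision to launch. If the larger trial starts only after a pilot significant in the favourable direction, then P(Z1 > 1.96 and |Z| > 1.96) = 0.0033. Among launched trials the error is 0.0033/0.025 = 13%; counting unlaunched trials it is 0.3%. Pooling also requires unchanged eligibility, randomisation, intervention, outcomes and timing. A sound rule must settle all of this, and most of it cannot be known until the larger trial is designed.

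**The case for a change.** The strongest case for a change is timing. The larger trial's protocol will probably be written by people who have seen the pilot results by arm. A pooling rule dated then is harder to show as independent of the effect than one dated before the first randomisation. The sponsor raised pooling in this document, so a condition could reasonably sit beside it. A recorded commitment would lose no patients. If the later trial were re-sized, a combination test with fixed weights 40/261 and 221/261 holds 5.0% and costs at most 0.3 points of power at totals of 200 to 400 (1.8 points at 120). The two-sided figures also understate the effect in the direction that matters: with the most favourable of three scores, error there reaches 4.6% against 2.5%.

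Much of this stands. The gap is real, no section fills it, and an early commitment is the simplest to defend. It does not follow that this protocol needs amending. A later protocol can still control error fully by keeping the 40 out of the confirmatory analysis, or by a method that allows for selection. Being included in an analysis does not mean naive pooling; a stratified, combination or sensitivity analysis would also satisfy the wording. An early commitment requires the endpoint to be named before the pilot has done the job it was set up for.

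**Conclusion.** No change to this plan. Section 9.2 grants a permission about data reuse. It does not specify an analysis, and nothing this pilot does or concludes depends on it. Harm needs a chain of later choices: a design decision driven by the pilot effect, then pooling without allowance, in a trial whose protocol does not yet exist and can set its own rule. Under the assumed total of 261, that chain gives two-sided error between 5.0% and about 6.9%. Error in the favourable direction is about 3.3% if data are pooled only after a favourable pilot, and up to 4.6% under the most adverse endpoint choice examined. These figures illustrate the size of the problem; the significance level, total, correlations and selection rules are not in the documents.

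Leaving the matter open is also a fair trade-off. An early rule would tie down the endpoint that the pilot is meant to inform, and its fallback costs about 7 points of power at 261, against a two-sided rise of zero to about two points.

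The matter belongs in the larger trial's protocol and SAP. There it should be settled whether pooling and the endpoint were fixed before any comparison by arm, whether launch and sample size depended on the pilot effect and how the analysis allows for that, and whether eligibility, randomisation, intervention, outcomes and timing stayed the same.

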## **10. QUALITY ASSURANCE PROCEDURES**

The study may be monitored, or audited in accordance with the current approved protocol, GCP, relevant regulations and standard operating procedures.

The CI administering the questionnaires will continually be present with the participants, which will ensure reliable, high quality data to be collected.

## **11. ETHICAL AND REGULATORY CONSIDERATIONS**

### **11.1. Declaration of Helsinki**

The Investigator will ensure that this study is conducted in accordance with the principles of the Declaration of Helsinki.

### **11.2. Guidelines for Good Clinical Practice**

The Investigator will ensure that this study is conducted in accordance with relevant regulations and with Good Clinical Practice.

### **11.3. Approvals**

The protocol and participant information sheet will be submitted to an appropriate Research Ethics Committee (REC), HRA, and host institution(s) for written approval.

The Investigator will submit and, where necessary, obtain approval from the above parties for all substantial amendments to the original approved documents.

### **11.4. Reporting**

The CI shall submit once a year throughout the study, or on request, an Annual Progress report to the REC Committee, host organisation and Sponsor. In addition, an End of Study notification and final report will be submitted to the same parties.

### **11.5. Participant Confidentiality**

The study staff will ensure that the participants' anonymity is maintained. The participants will be identified only by a participant ID number on all study documents and any electronic database, with the exception of the CRF, where participant initials may be added. All documents will be stored securely and

only accessible by study staff and authorised personnel. The study will comply with the Data Protection Act, which requires data to be anonymised as soon as it is practical to do so.

### **11.6. Expenses and Benefits**

Each participant will receive £10 for their time taking part in the study, upon completion of the last questionnaire (visit 2). This has been determined on the basis of previous studies published in the literature.

### **11.7. Other Ethical Considerations**

The intervention has been developed in collaboration with both health professionals and patients. Although some patients might find risk communication distressing, the intervention has been designed to be as patient-friendly as possible and will be conducted by patients' personal GP. Patients will be encouraged to share any concern with their GP.

## **12. FINANCE AND INSURANCE**

### **12.1. Funding**

The research is supported by the University of Oxford ('Oxford-Health Economics Research Centre Graduate Scholarship').

### **12.2. Insurance**

The University has a specialist insurance policy in place which would operate in the event of any participant suffering harm as a result of their involvement in the research (Newline Underwriting Management Ltd, at Lloyd's of London). NHS indemnity operates in respect of the clinical treatment that is provided.

## **13. PUBLICATION POLICY**

The Investigators will be involved in reviewing drafts of the manuscripts, abstracts, press releases and any other publications arising from the study. Authors will acknowledge that the study was funded by the National Institute for Health Research (NIHR) Collaboration for Leadership in Applied Health Research and Care Oxford at Oxford Health NHS Foundation Trust. Authorship will be determined in accordance with the ICMJE guidelines and other contributors will be acknowledged.

Amendment table				
Amendment number	Protocol number	Date	Author	Description

